#### 10.4.2 ANALYSIS OF THE PRIMARY EFFICACY OUTCOME(S)

The number of bleeding events up to day 7 will be analysed in terms of a risk difference between the two treatment groups, using the methods described by Cui, Hung & Want (1999).

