#### 3 OBJECTIVES AND PURPOSE

#### Primary objective:

• To evaluate whether TXA mouthwash 10% reduces the number of oral bleeding events in patients treated with NOACs and undergoing dental extraction.

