#### 4.2.1 PRIMARY OUTCOME

• Any oral bleeding (early or delayed; minor or clinically relevant)

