#### 10 STATISTICAL CONSIDERATIONS

#### 10.1 STATISTICAL AND ANALYTICAL PLANS

There is no external statistical and analytical plan.

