#### 10.2 STATISTICAL HYPOTHESES

This is a superiority study. The null hypothesis is that there is no difference in any oral bleeding between the intervention group and the control group (primary outcome).

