#### 10.4.3 ANALYSIS OF THE SECONDARY OUTCOME(S)

 The number of all different type of bleeding events, number of reinterventions and number of unplanned NOAC interruptions in the TXA group and placebo group will be compared using the Fisher Exact Test or Chi Square test, depending on the number of events. The effect of treatment will be estimated by the risk difference and presented along with its associated 95% confidence interval.

The procedural bleeding score in the TXA group and placebo group will be compared using the Student ttest of Mann-Whitney U-test, as appropriate. The effect of treatment will be estimated by the difference between treatments and presented along with its associated 95% confidence interval.

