#### 10.4.4 SAFETY ANALYSES

 The number of non-oral bleeding, allergic reactions and thrombotic complications in the TXA group and placebo group will be compared using the Fisher Exact Test or Chi Square test, depending on the number of events.

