#### 10.5 SAMPLE SIZE

- Based on the previously cited pilot study, we estimate the rate of the primary outcome at 30% in the placebo group (7).
- We estimate to show an absolute risk reduction (ARR) of 15% This means an incidence of 15% in the tranexamic acid group.
- Confidence level is set to 95%, power is set to 80%.
- Under the above assumptions, in order to have 80% to detect a statistically significant risk difference between treatments, 118 patients per group or 236 patients in total will be required.

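### Does the primary analysis count bleeding events rather than patients who bled?

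*Combined protocol and SAP*

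**What the plan says.** Two sets of wording run through the combined protocol and SAP.

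**Event wording.** The primary objective in Section 3 asks whether "TXA mouthwash 10% reduces the number of oral bleeding events in patients treated with NOACs" and undergoing extraction, and the Protocol Summary says the same. Section 10.4.2 then gives the primary analysis: "The number of bleeding events up to day 7 will be analysed in terms of a risk difference between the two treatment groups". Section 10.4.3 uses similar language for the secondary outcomes ("The number of all different type of bleeding events, number of reinterventions and number of unplanned NOAC interruptions"), as does Section 10.4.4 for safety ("The number of non-oral bleeding, allergic reactions and thrombotic complications"). Both send these to Fisher's exact or chi-square tests.

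**Patient wording.** Section 4.2.1 defines the primary outcome as "Any oral bleeding (early or delayed; minor or clinically relevant", closing the bracket there. Section 10.2 states: "The null hypothesis is that there is no difference in any oral bleeding between the intervention group and the control group". Section 10.3 analyses all randomised patients by assigned arm. Section 10.4.1 names the risk difference with its 95% confidence interval as the primary effect estimate. Section 10.5 says "we estimate the rate of the primary outcome at 30% in the placebo group" and assumes an incidence of 15% on tranexamic acid, giving 118 patients per group.

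Section 10.1 adds: "There is no external statistical and analytical plan". Section 10.4.7.2 promises an Interim Statistical Analysis Plan for the sample size re-estimation.

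**The concern.** A number of events is not a risk. Section 10.4.2 therefore names one kind of variable and an effect measure that belongs to another, in the sentence that defines the primary analysis. Repeat bleeds are foreseeable. Section 4.2 separates early bleeding (to day 1) from delayed bleeding (day 2 to day 7), bleeding is asked about at both telephone calls, and minor bleeding covers signs that can easily recur. No section says that such a patient counts once.

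If total events were divided by patients and tested as a proportion, the variance would be too small and the false-positive rate too high. The event-based and patient-based tests could also disagree. With 10% to 50% of bleeders bleeding twice, simulation of a fixed trial with 118 per arm finds disagreement on significance in about 5% to 14% of trials under no effect, 11% to 21% at 30% versus 20%, and 7% to 11% at the planned 30% versus 15%. The conditional power behind the sample size re-estimation would rest on the same unit.

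**Working it through.** **1. Reproduce the plan's sample size as a per-patient comparison.** Inputs: 30% and 15%, 80% power (Section 10.5); two-sided 5% (Section 10.4.1).

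- Formula: n per group = (z₀.₉₇₅ + z₀.₈₀)² × [p₁(1 − p₁) + p₂(1 − p₂)] / (p₁ − p₂)²
- Variance term: 0.30 × 0.70 + 0.15 × 0.85 = 0.3375
- (1.95996 + 0.84162)² = 7.849
- n = 7.849 × 0.3375 / 0.0225 = 117.7, so 118 per group and 236 in total, as planned. Power at 118 is 80.1%.

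The pooled-variance version gives 121 per group. Both versions treat each patient as a single yes or no.

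**2. Compare with a count-based calculation.** Suppose 0.30 and 0.15 were mean events per patient, with Poisson variance equal to the mean (an assumption made only for this contrast). Then n = 7.849 × (0.30 + 0.15) / 0.0225 = 157 per group. The plan's 118 does not come from that.

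**3. Apply the outcome definition to each bleeding pattern.**

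| Early bleed | Delayed bleed | Any oral bleeding |
|---|---|---|
| no | no | no |
| yes | no | yes |
| no | yes | yes |
| yes | yes | yes, once |

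The definition already gives one value per patient. The data collection in Sections 7.3.3 and 7.3.4 fits this: each call records yes/no bleeding items and one line for date and time, with no field for the number of bleeds.

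**4. Size of the error under the event reading.** Let 30% of patients bleed in both arms, and let a fraction q of bleeders have a second event. The documents give no value for q.

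- Mean events per patient: m = 0.30(1 + q)
- True variance: V = 0.30(1 + 3q) − m²
- Variance a proportion test would use: B = m(1 − m)
- Type I error ≈ 2 × [1 − Φ(1.96 / √(V/B))]

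| q | m | V | B | V/B | Type I error |
|---|---|---|---|---|---|
| 0.10 | 0.33 | 0.2811 | 0.2211 | 1.27 | 8.2% |
| 0.20 | 0.36 | 0.3504 | 0.2304 | 1.52 | 11.2% |
| 0.50 | 0.45 | 0.5475 | 0.2475 | 2.21 | 18.8% |

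Simulation (200,000 trials per scenario, 118 per arm, interim ignored) agrees: 8.2%, 11.3% and 19.3%. In the same simulations the per-patient test stays at 5.0% to 5.1%. An event-based test using the variance between patients stays at 5.0% to 5.2%. The excess therefore comes from putting a binomial variance on repeat events. Section 10.4.2 does not prescribe that; it names a risk difference and the Cui, Hung and Wang method.

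**5. Interim.** That method combines the stage-wise statistics of the primary comparison, so the interim and final analyses share one unit. Section 10.4.7.2 places its details in the Interim Statistical Analysis Plan, which is not among the documents.

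**The case for a change.** The strongest case for a change is that an analysis plan should not leave the unit of its primary test to inference, least of all when it is the only plan and one sentence would remove the doubt. If patients are meant, the objective as worded has no matching analysis. If events are meant, the Fisher and chi-square tests in Sections 10.4.3 and 10.4.4 do not fit.

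Part of this stands. The wording is inconsistent, and nowhere does the plan say outright that each patient counts once. The arithmetic on inflated type I error is also right under its assumptions.

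It does not carry further. The outcome definition says how the objective is measured, and it is a status per patient. A two-by-two test needs one yes or no per patient, so the counts in Sections 10.4.3 and 10.4.4 read as ordinary shorthand for patients with the event; Section 10.4.3 also reports a risk difference. The inflation requires an unsourced repeat rate and a variance that the primary analysis section does not call for. A count model over the early and delayed windows would not serve the literal objective either, because several delayed bleeds in one patient would count as one.

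**Conclusion.** The concern does not call for a change. The event wording in Sections 3 and 10.4.2 to 10.4.4 is a clerical looseness that analysts will resolve correctly. The outcome, the hypothesis, the effect measure and the sample size all point to the proportion of randomised patients with any oral bleeding up to day 7. Under that reading N stays at 236, power at about 80% and type I error at about 5% for a fixed sample.

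The 8% to 19% figures describe an analysis that the plan does not specify, at assumed repeat rates of 10% to 50% among bleeders. The conclusion assumes that the Interim Statistical Analysis Plan uses the same per-patient outcome, as Section 10.4.2 implies by naming the same method. Stating the unit outright would be tidier but would alter no result.

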#### Exploratory analyses:

- To investigate the potential relationship between time of last NOAC dose administered prior to the extraction (regardless of specific NOAC type), time of resuming NOAC after the procedure, and bleeding events
- To investigate the potential benefit of TXA in subgroups of patients (molar versus non-molar extraction)

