#### 7.1.2 STANDARD OF CARE STUDY PROCEDURES

- No NOAC dose is to be taken on the day of the procedure
- Dental extraction is then performed according to the current and local standard-of-care, at the discretion of the treating physician. The use of additional hemostatic measures is permitted but will be recorded.
- Patients will be instructed to restart the NOAC the day after the extraction, according to current standard-of-care.
- Any other antithrombotic medication is to be continued

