#### 7.3.2 ENROLLMENT/BASELINE

- Assess patient characteristics:
  - o Age
  - Sex
  - Date of birth
  - Alcohol and tobacco use
  - Phone number for follow-up calls
  - NOAC type: rivaroxaban, apixaban, dabigatran, edoxaban
  - NOAC dose and regimen
  - NOAC indication
  - Date and time of last NOAC dose
  - Serum creatinine when available (up to 12 months before inclusion)
  - Other antithrombotic drugs: aspirin (Asaflow®, Cardio-aspirine®), clopidogrel (Plavix®), ticagrelor (Brilique®), prasugrel (Efient®), dipyridamole (Aggrenox®), LMWH
  - Non-steroidal anti-inflammatory drug use (eg. ibuprofen)
  - o Record full list of medication in the medical file
- Administer the study treatment
- Perform dental extraction
- Assess procedure characteristics:
  - o Date and time of extraction
  - Number of extracted teeth
  - Teeth numbers
  - Stitches: yes/no
  - Persistent infection: yes/no
  - Burring: yes/no
  - Procedural bleeding score (0-10)
  - o Use of additional hemostatic measures: eg. tranexamic acid gauze
  - o Prophylactic antibiotics: yes/no
- Instructions to patient:
  - Supply patient with 9 vials of mouthwash
  - Supply patients with instructions to perform mouthwash starting 1 day after extraction, 3 times a day for 3 days
  - Instruct patients to restart NOAC the day after the extraction according to their normal regimen
  - Instruct patients to write down any signs of bleeding

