#### 10.4.7.2 EFFICACY REVIEW

After 100 patients have reached their 7-day visit, an efficacy review is planned to reassess the required sample size. This will be done using the methods described by Cui, Hung & Wang (1999). The sample size re-estimation (SSR) will be based on the observed conditional power at the time of the interim analysis. The re-estimated sample size will be required to be between 150 and 300 patients. Full details for the methodology of the SSR will be provided in an Interim Statistical Analysis Plan.

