#### 10.4.8 ADDITIONAL SUB-GROUP ANALYSES

A number of exploratory subgroup analyses is planned, for which the study is not powered, including:

- The number of bleeding events in patients who resumed their NOAC treatment within 24 hours after extraction compared to later than 24 hours after extraction, stratified per treatment group.
- Risk factor analysis for bleeding, eg. patient demographics and procedural characteristics

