#### 10.6 MEASURES TO MINIMIZE BIAS

#### 10.6.1ENROLLMENT/ RANDOMIZATION/ MASKING PROCEDURES

A computer-generated block-randomization list will be generated by an independent person for treatment allocation. Labeling of the study drug and matched placebo will occur by an independent person. Sealed envelopes will contain patient number and randomization group.

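### Does the primary risk difference need adjustment for baseline bleeding risk factors?

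*Combined protocol and SAP*

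**What the plan says.** Section 10.4.2 says that bleeding up to day 7 "will be analysed in terms of a risk difference between the two treatment groups", with the Cui-Hung-Wang method to protect the type I error. Section 10.4.1 adds a 95% confidence interval for that difference. Neither section names a covariate, and section 10.1 says "There is no external statistical and analytical plan", so section 10 is the operative text for the primary test.

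On allocation, section 10.6.1 says "A computer-generated block-randomization list will be generated by an independent person for treatment allocation". It gives no stratification factor.

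Possible predictors of bleeding appear elsewhere:

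- Section 7.1.2: "Any other antithrombotic medication is to be continued". Section 7.3.2 records these drugs as patient characteristics.
- Section 7.3.2 also records "Number of extracted teeth" and tooth numbers, under procedure characteristics.
- Section 3 lists an exploratory look at TXA benefit by molar versus non-molar extraction.
- Section 10.4.8 plans, as exploratory work, "Risk factor analysis for bleeding, eg. patient demographics and procedural characteristics".

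Section 10.4.7.2 sets a re-estimation after 100 patients: "The re-estimated sample size will be required to be between 150 and 300 patients".

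**The concern.** The protocol expects some patients to bleed more than others and collects data on who they might be, yet uses none of it in the primary comparison. Randomisation is not described as stratified, so neither design nor analysis deals with a chance imbalance. With a binary outcome and about 53 expected events (118 × 0.30 + 118 × 0.15 = 35.4 + 17.7), a statistician will naturally ask whether precision is being given away.

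Two things would be at stake: power for the 15-point reduction, and the credibility of the estimate if one arm happened to receive more difficult extractions. Timing matters too. A covariate set chosen after the unblinded interim would be open to challenge.

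**Working it through.** **1. Does the plan's own sample size match an unadjusted test?** Inputs from sections 10.4.1 and 10.5: 30% versus 15%, two-sided 5%, power 80%.

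n per group = (1.960 + 0.842)² × (0.30 × 0.70 + 0.15 × 0.85) / 0.15² = 117.7, rounded up to 118.

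This is the stated figure. The trial was sized for the analysis it plans.

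**2. Is the crude estimate biased?** No. Randomisation makes the difference in observed proportions unbiased for the marginal risk difference. In a fixed-design simulation (6,000 trials per setting, N = 236) the crude and the logistic-standardised estimates were both centred on -0.15. As no stratification factor is named, there is none that the analysis would have to carry.

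**3. What could adjustment add in a fixed design?** SE = √[(0.21 + 0.1275)/118 × (1 − R²)], where R² is the share of outcome variance explained. The documents give no R², so a range is assumed.

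| R² | 95% CI half-width (points) | Power | Equivalent N, 236/(1 − R²) |
|---|---|---|---|
| 0 | 10.5 | 80.1% | 236 |
| 0.02 | 10.4 | 80.9% | 241 |
| 0.05 | 10.2 | 82.1% | 248 |
| 0.10 | 9.9 | 84.1% | 262 |

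This formula charges nothing for estimating coefficients. In the step 2 simulation, with three binary covariates sharing an odds ratio of 1.0, 1.5, 2.0 or 3.0, relative efficiency was 0.99, 1.01, 1.03 and 1.11.

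**4. What could it add under the planned adaptive design?** Simulations used stage 1 = 100 and fixed weights √(100/236) and √(136/236). Assumed prevalences: molar 50%, antiplatelet 20%, teeth 1 + Poisson(1). Re-estimation used an assumed 80% conditional-power target at the observed effect and total N of about 150 to 300. Where two figures appear for the fixed second stage, they come from two separate runs.

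| Assumed odds ratios (molar / per tooth / antiplatelet) | Power change with re-estimation (points) | Power change, second stage fixed at 136 (points) |
|---|---|---|
| none | -0.5 | -1.0, -0.8 |
| 1.5 / 1.2 / 1.5 | +0.1 | -0.2, 0.0 |
| 2 / 1.35 / 2 | +1.1 | +1.1 |
| 2.5 / 1.6 / 2 | +1.9 | +2.1, +2.4 |

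Mean N was 220 to 224 with or without adjustment, and type I error was 5.0 to 5.6% for both.

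**5. Which covariates are usable as the protocol stands?** Section 7.3.2 lists the tooth fields after study treatment and extraction, so as recorded they are not pre-randomisation values. Using them safely would need a new item for the planned extraction. A plan also differs from what is done: with an assumed 15% discordance, gains of +0.9 and +2.3 points in the two strongest settings fell to about +0.3 and +1.6. Other antithrombotic use is patient history and could be used, but alone it changes power by only -0.4 to +0.2 points.

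**6. How much could chance imbalance matter?** With 50% molar prevalence (assumed), the SE of the arm difference at 118 per arm is √(2 × 0.25/118) = 6.5 points. A gap of 10 points or more in either direction therefore has probability about 12%, and about 6% in the direction that favours TXA. In that case the crude estimate shifts by 1.1 to 1.8 points across the three prognostic settings, which is 10% to 17% of the 10.5-point half-width. The confidence interval already allows for this kind of chance variation.

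**The case for a change.** The best case for adjustment is a fair one. A standardised adjusted analysis targets the same marginal risk difference, leaves the type I error unchanged, and cuts the imbalance shift in step 6 to 0.2 points or less. It would cost some plan wording and one small data item. Section 10.4.7.2 leaves the re-estimation details to an Interim Statistical Analysis Plan, which gives a natural place for the choice.

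All of that stands as a description of an option. It does not show that the current choice is wrong, for three reasons.

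- The documents do not establish that any factor is prognostic. Section 10.4.8 sets out to look for risk factors. The molar question in section 3 is about whether the treatment effect differs, which is not the same as prognosis. With no covariate-bleeding association stated, even the sign of the gain rests on assumed odds ratios.
- Adjustment complicates the adaptive test. The same adjusted statistic would have to drive the interim conditional power and the final weighted test, with a matching confidence interval. The variance ratios that suggest a narrower interval (1.016 to 0.940 at N = 236) come from pooled standardisation, so the gain in width for a matched interval has not been shown.
- The design has a larger lever for precision. In the two strongest settings the variance ratios of 0.963 and 0.940 are worth about 9 and 15 patients (236/0.963 = 245; 236/0.940 = 251). The re-estimation ceiling of 300 allows 64 more than planned.

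**Conclusion.** The concern does not hold. The crude risk difference is a valid, prespecified analysis that matches the sample size calculation exactly. Adjustment would trade a loss of about half a point to one point of power, if the factors are not prognostic, for a gain of about one to two and a half points under the two strongest settings assumed. On the data collection now described, the only proposed clinical covariate available as patient history yields essentially no gain.

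This rests on the assumed prevalences, odds ratios and conditional-power target above, none of which the documents supply. Much stronger predictors would raise the gain: a common odds ratio of 3 for all three covariates took power from 80.8% to 85.0% in the fixed design. Even then the unadjusted analysis would remain valid, only less efficient. The conclusion concerns the absence of covariates alone. It does not address how the confidence interval is to be built after re-estimation.

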#### 10.4.3 ANALYSIS OF THE SECONDARY OUTCOME(S)

 The number of all different type of bleeding events, number of reinterventions and number of unplanned NOAC interruptions in the TXA group and placebo group will be compared using the Fisher Exact Test or Chi Square test, depending on the number of events. The effect of treatment will be estimated by the risk difference and presented along with its associated 95% confidence interval.

The procedural bleeding score in the TXA group and placebo group will be compared using the Student ttest of Mann-Whitney U-test, as appropriate. The effect of treatment will be estimated by the difference between treatments and presented along with its associated 95% confidence interval.

#### 10.4.4 SAFETY ANALYSES

 The number of non-oral bleeding, allergic reactions and thrombotic complications in the TXA group and placebo group will be compared using the Fisher Exact Test or Chi Square test, depending on the number of events.

#### 10.4.5 ADHERENCE AND RETENTION ANALYSES

No formal testing for adherence is planned, but the number of vials of the study drug will be recorded. Compliance will be calculated as the total number of vials taken divided by the required number of vials. Patients with less than 80% compliance will be excluded from the Per Protocol Set.

#### 10.4.6 BASELINE DESCRIPTIVE STATISTICS

Baseline characteristics will be presented by randomized treatment group, using appropriate summary statistics.

#### 10.4.7 PLANNED INTERIM ANALYSES

#### 10.4.7.1 SAFETY REVIEW

After inclusion of 100 patients, a safety reviewed is planned to assess thrombotic events, allergic reaction and non-oral bleeding.

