#### 2.3 POTENTIAL RISKS AND BENEFITS

#### 2.3.1 KNOWN POTENTIAL RISKS

Potential risks of systemic administration of TXA, as reported by the package insert, include convulsions, blurred vision, haematuria and thrombo-embolism. However, none of these potential risks have been shown to be present in case of mouthwash as compared to systemic administration (10). This can be explained by the low systemic TXA levels in case of administration by mouthwash (9).

Therefore, the immediate potential risk of TXA mouthwash is limited to:

- Allergic reaction
- Bleeding in case of extensive or traumatic mechanical rinsing

There are no known long-term risks. Because of these limited potential risks, the potential benefit of this treatment is expected to outweigh the risks.

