#### 8.5 STUDY HALTING RULES AND SAFETY OVERSIGHT

Interim analysis will be performed after inclusion of 100 patients to assess thrombotic events, allergic reaction and non-oral bleeding.

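### The 100-patient safety review does not list oral bleeding, one of the two immediate risks named for the mouthwash, and the parallel efficacy review states no action if TXA looks worse

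*Combined protocol and SAP*

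**What the plan says.** Section 2.3.1 of the protocol limits the immediate risks of the mouthwash to two: "Allergic reaction" and "Bleeding in case of extensive or traumatic mechanical rinsing".

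Two reviews are tied to the first 100 patients.

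- **Safety review.** Under the halting-rules heading, section 8.5 says: "Interim analysis will be performed after inclusion of 100 patients to assess thrombotic events, allergic reaction and non-oral bleeding". Section 10.4.7.1 repeats the same three items: "a safety reviewed is planned to assess thrombotic events, allergic reaction and non-oral bleeding". The trigger is inclusion of 100 patients.
- **Efficacy review.** Section 10.4.7.2 says: "After 100 patients have reached their 7-day visit, an efficacy review is planned to reassess the required sample size". It continues: "The sample size re-estimation (SSR) will be based on the observed conditional power at the time of the interim analysis", and "The re-estimated sample size will be required to be between 150 and 300 patients". The method is deferred to an Interim Statistical Analysis Plan.

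The primary outcome (4.2.1) is any oral bleeding, minor or clinically relevant. Section 4.2 grades severity: minor needs no medical contact, clinically relevant non-major needs unplanned contact, and major means transfusion, hospitalization or death. Section 4.2.2 counts both non-major and major events as clinically relevant.

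**The concern.** One of the two named risks is on the safety list and the other is not. The word non-oral excludes bleeding at the extraction site, where rinsing acts. As written, the only scheduled safety look does not include major oral bleeding, the most serious form of the event under study.

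The efficacy review does not fill the gap. Its stated purpose is sample size. It works on a pooled yes/no outcome in which blood on the pillow counts the same as a hospitalization. It states no harm boundary, no futility boundary and no action on a reversed effect. An excess of clinically relevant or major oral bleeding on TXA could therefore be present at 100 patients without the plan requiring anyone to look at it as safety information before the sample size is reset.

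**Working it through.** **1. The lists side by side**

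| Event | Immediate mouthwash risk in 2.3.1 | Safety review (8.5, 10.4.7.1) | Efficacy review (10.4.7.2) |
|---|---|---|---|
| Allergic reaction | yes | yes | no |
| Oral bleeding, all severities pooled | yes (from rinsing) | no | yes, as input to sample size |
| Clinically relevant or major oral bleeding, shown separately | not separated | no | no |
| Thrombotic events | no | yes | no |
| Non-oral bleeding | no | yes | no |

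The omission is visible without any assumption.

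**2. Why the pooled outcome is not enough.** If 15 of 50 patients bleed in each arm (30%), the interim statistic is z = 0 however those 15 divide between minor, clinically relevant and major. A shift in severity with equal totals does not show.

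**3. The planned sample size reproduces.** Inputs from 10.5 and 10.4.1: 30% versus 15%, two-sided 5%, power 80%. Unpooled normal approximation:

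n = (1.960 + 0.842)² × (0.30×0.70 + 0.15×0.85) / 0.15² = 7.849 × 0.3375 / 0.0225 = 117.7, so 118 per arm and 236 in total, as stated.

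**4. What the re-estimation does if TXA looks worse.** The documents give no interim rates, so these are assumed: placebo 30%, TXA 36% to 50%, 50 patients per arm. With the Cui-Hung-Wang fixed weights, w₁ = √(100/236) = 0.651 and w₂ = √(136/236) = 0.759. For total size N, at the observed trend:

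- z₁ = (p_placebo − p_TXA) / √(2p̄(1 − p̄)/50)
- m = z₁ × √((N − 100)/100)
- conditional power for benefit = 1 − Φ[(1.96 − w₁z₁)/w₂ − m]
- conditional power for harm = Φ[(−1.96 − w₁z₁)/w₂ − m]

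Example, TXA 40%, N = 300: z₁ = −0.10/√(2×0.35×0.65/50) = −1.05 and m = −1.48. Benefit: 1 − Φ(3.48 + 1.48), below 0.1%. Harm: Φ(−1.68 + 1.48) = 42%.

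| Assumed TXA rate | z₁ | Benefit, any N from 150 to 300 | Either direction at N = 150 / 236 / 300 | N giving 80% in either direction |
|---|---|---|---|---|
| 36% | −0.64 | <0.1% | 5.7% / 9.8% / 12.9% | none up to 300 |
| 40% | −1.05 | <0.1% | 17% / 32% / 42% | none up to 300 |
| 46% | −1.65 | <0.1% | 50% / 77% / 88% | 249 |
| 50% | −2.04 | <0.1% | 73% / 94% / 98% | 168 |

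No permitted N rescues conditional power for benefit, so the result turns on the unstated rule:

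- raising N until 80% or the cap gives 300;
- a promising-zone rule leaves 236;
- a rule that does not invest in an unfavourable zone could give 150;
- a two-sided rule could give 249 or 168 in the last two rows.

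**5. What a by-arm table could show at this point.** With 50 per arm and two-sided 5%, power = Φ[(d − 1.96√(2p̄(1 − p̄)/50)) / √((p₁q₁ + p₂q₂)/50)]. For 30% versus 40%: Φ[(0.100 − 0.187)/0.0949] = Φ(−0.92) = 18%. For 30% versus 45%: Φ[(0.150 − 0.190)/0.0957] = Φ(−0.42) = 34%. Rarer clinically relevant or major events would be less informative.

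**6. Timing.** Section 4.2 defines delayed bleeding as days 2 to 7. A review triggered at inclusion could precede part of that window for the latest patients, whereas the efficacy review waits for day 7.

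**The case against.** Keeping the primary efficacy outcome off a safety list is a defensible choice, and four points on that side have weight.

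- **Other routes exist.** Hospitalization and death are serious adverse event criteria (8.1.2), events are assessed at days 2 and 7 (8.3), and section 5.5 allows suspension for unacceptable risk. It would be wrong to say that serious oral bleeding goes unseen. But these routes work case by case or at discretion. They do not schedule a comparison by severity, and bleeding that only prompts a phone call or visit need not be serious in the regulatory sense.
- **Oral bleeding by arm is examined at the interim anyway**, because conditional power needs it, and clinically relevant events are counted in it. This stands, but they are not shown separately and the stated purpose is sample size.
- **Both arms rinse** (7.1.1), so a by-arm comparison may largely cancel the mechanical risk that 2.3.1 names. This stands, and it is why the table must also show overall rates.
- **Arm-level bleeding data at an interim put the blind at risk**, and section 15.1 gives oversight to the principal investigator. This stands and is met by restricting access.

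A reader might also infer that the efficacy review would enlarge the trial if TXA increased bleeding. The documents do not support that. Section 10.4.7.2 allows a decrease, no change or an increase, and leaves the rule to a document not available here. Under one assumed rule (smallest N from 150 to 300 reaching 80% conditional power for benefit, otherwise 300), simulated interims with placebo at 30% go to 300 in about 99.5% of cases with TXA at 40%. They also do so in about 93% with no effect at all, so the figure mostly describes that assumed rule.

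**Conclusion.** The point holds as a gap in scheduled review. Oral bleeding is absent from the 100-patient safety review in both places where its content is given, although bleeding from rinsing is one of the two immediate risks named. The efficacy review pools severities and states no action if TXA looks worse. This rests on the text alone.

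The direction of any sample-size change after an unfavourable interim is undetermined. Under the assumed rates and rules above it ranges over the whole permitted span, so enlargement is possible but not established.

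This is a low-cost improvement. It does not threaten the primary analysis, and with about 50 patients per arm the added table would inform judgement rather than test a hypothesis.

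**What to change.** - In 8.5 and 10.4.7.1, add adjudicated clinically relevant oral bleeding (non-major and major), major oral bleeding alone, and reinterventions to the events assessed at the 100-patient safety review. Tabulate them both overall and by arm.
- Run that review on 100 patients who have completed day 7, so that it covers delayed bleeding and uses the same patients as the efficacy review.
- Restrict the by-arm tables to people not involved in treating or assessing patients.
- In 10.4.7.2, state that any sample-size change is enacted only after the safety review is complete.
- In the Interim SAP, before the interim, state whether conditional power is one- or two-sided, its target and zones, and how an observed difference favouring placebo is handled.

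No stopping threshold is proposed; that is for the sponsor and its safety reviewers.

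The cost is a line in each of two sections, a sentence in a third and one table. The data are already collected at the day 2 and day 7 calls (7.3.3, 7.3.4) and adjudicated blind (4.2). The practical burden is having adjudication finished for the first 100 patients and arranging restricted access.
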